2.1. Definition of Relationship of AE to the Investigational Medicinal Product

The Investigator will also be asked to assess the possible relationship between the AE and the investigational medication. The relationship should be assessed according to the following criteria:

Relationship of the Adverse Event to the Investigational Medicinal Product

None (Intercurrent Event)

An event that is not and cannot be related to the Investigational Medicinal Product, e.g. patient is a passenger in a road traffic accident.

Unlikely (remote)

Relationship is not likely e.g. a clinical event including laboratory test abnormality with temporal relationship to drug administration which makes a causal relationship improbable and in which other drugs, chemicals or underlying disease provide plausible explanations.

Possible Relationship may exist, but could have been produced by the patient's condition or treatment or other cause.

Probable

Relationship is likely; the adverse event abates upon discontinuation of Investigational Medicinal Product and cannot be due to the patient's condition.

Highly Probable

Strong relationship, the event abates upon discontinuation of Investigational Medicinal Product and, if applicable, re-appears upon repeat exposure.

2.2. Definition of Severity of Adverse Events

Severity of any AE will be graded according to National Cancer Institute (NCI) Common Toxicity Criteria (CTC) version 3.0, where applicable. For each episode, the highest severity grade attained should be reported. If an AE occurs that is not listed in the CTC, the Investigator will evaluate its severity using the following criteria:

Definition of Severity of Adverse Events

Mild Grade 1 - Does not interfere with subject's usual function (awareness of symptoms or signs, but easily tolerated [acceptable]).

Moderate Grade 2 - Interferes to some extent with subject's usual function (enough discomfort to interfere with usual activity [disturbing]).

Severe Grade 3 - Interferes significantly with subject's usual function (incapacity to work or to do usual activities [unacceptable])

Life Threatening Grade 4 - Results in risk of death, organ damage, or permanent disability (unacceptable)

Note the distinction between the seriousness and the intensity of an AE. **Severe** is a measure of intensity; thus, a **severe** reaction is not necessarily a **serious** reaction. For example, a headache may be severe in intensity, but would not be classified as serious unless it met one of the criteria for serious events listed in section 3.

2.3. Frequency of Adverse Events

Once The AE occurred only once and cleared in < 24 hours.

Occasionally The AE occurred sporadically or episodically between the onset and clearance dates.

Continuously The AE was present for the entire time between onset and clearance dates and was > 24 hours duration.

3. Serious Adverse Events

3.1. Definition of a Serious Adverse Event

A Serious Adverse Event is defined as any untoward medical occurrence that at any dose:

- Results in death.
- Is life-threatening (i.e. the patient was at risk of death at the time of the event. It does not refer to an event which hypothetically might have caused death if it were more severe).
- Requires inpatient hospitalisation or prolongation of existing hospitalisation.
- Results in persistent or significant disability/incapacity.
- Is a congenital anomaly/birth defect.

Medical and scientific judgement should be exercised in deciding whether expedited reporting is appropriate in other situations, such as important medical events that may not be immediately lifethreatening or result in death or hospitalisation but may jeopardise the patient or may require intervention to prevent one of the other outcomes listed above. These should also usually be considered serious. Examples of such events are intensive treatment in an emergency room or at home for allergic bronchospasm; blood dyscrasias or convulsions that do not result in hospitalisation; or development of drug dependency or drug abuse.

3.2. SAE Reporting Procedure for Investigators to Sponsor

The Investigator must report all SAE, regardless of presumed causal relationship, to the Promotor by fax on a Serious Adverse Event form within 24 hours of learning of the event. Details of the relevant fax number for SAE will be provided as a separate document.

Information on Serious Adverse Events

Adverse Events (SAE) will be recorded on a specific Non Carbon Repeat (NCR) SAE form. Blank copies are included in the trial Investigator's File. The Investigator should follow up the event until resolution or stabilisation of the condition. Follow-up reports (as many as required) should be completed and faxed following the same procedure above.

A final report is required in any case once the condition is resolved or stabilised and no more information about the event is expected. The final report should be completed and faxed following the same procedure above.

4. Adverse Event Reporting Period

All AE that occur during the treatment period i.e. from the date of written informed consent to the final trial visit will be recorded in the CRF. In addition, any known untoward event that occurs subsequent to the AE reporting period that the Investigator assesses as possibly, probably or highly probably related to the Investigational Medicinal Product should also be reported as an AE.

XIX. QUALITY OF LIFE

Quality of life (QOL) will be measured by the general thirty-question EORTC quality of life questionnaire QLQ-C30. QOL is measured at baseline and every 3 months the first year (treatment period) and every 6 months the second year. Patients who withdraw will have a QOL assessment at discontinuation. These discontinuation data will be listed, but will not be included in tables or analyses. Every effort must be made to complete the QOL questionnaire. Where a whole questionnaire has not been completed but the patient has survived to the appropriate time, one of the following options will be recorded on the CRF.

- 1 = patient felt too ill
- 2 = clinician or nurse felt the patient was too ill
- 3 = patient felt it was inconvenient, takes too much time
- 4 = patient felt it was a violation of privacy
- 5 = patient didn't understand the actual language/ illiterate
- 6 = administrative failure to distribute the questionnaire to the patient
- 7 = other, please specify

For codes 1 or 2, data will be regarded as 'missing too ill' whereas for any of the other

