Treatment will be started 7 to 10 days before each TACE course for a total of 28 days per cycle with a three days interruption: from the day preceding to the day following each TACE. Total treatment duration will be one year (8 cycles). Treatment will be discontinued in case of documented tumor relapse or progression.

Study drugs will be given in the morning with water and without regard to meals beginning.

TACE modalities

The use of Doxorubicin Coated Beads (DC Beads) has been retained on the basis of the PRECISION V study. This randomised study compared conventional TACE with doxorubicin to TACE with DC Beads (23). Although the overall tumor response rate achieved by DC Beads was not significant superior ($p = 0.11$), it was significantly higher in some subgroups of patients (especially ECOG 1 patients and patients with bilobar disease). Additionally, the use of DC Beads appeared safer, especially with significantly reduced liver toxicity (3 vs. 9 %). Finally, a theoretical advantage for using DC Beads is that this method is standardized and more reproducible than conventional TACE.

The investigators must perform pre-treatment angiography to confirm the vascular anatomy and exclude significant arteriovenous shunting and are encouraged to identify and protect the cystic artery and gastric arteries.

TACE in HCC using DC beads should respect the following guidelines: 1 vial 300-500 micron followed by 1 vial 500-700 micron with a target dose of 150mg doxorubicin.

Beads are mixed with non-ionic contrast media or saline at a ratio of one to 5 to ensure smooth delivery through the catheter. The beads should be delivered slowly, approximately 1mL per minute, to minimise reflux and clogging within the catheter. A microcatheter is

recommended to obtain as superselective position as possible, namely in case of patients with finite number of tumors.

Patients with finite number of tumors should be treated in order to deliver the full dose of doxorubicin to the target lesion if single, or to divide the dose between them, if several. Treatment must be repeated with the same schedule at least twice. The use of a microcatheter to obtain selective catheterization of the feeding artery(ies) is recommended. No additional embolization is recommended after the use of DC beads in order to leave the artery patent for a second course.

[figure not shown]

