- Number and percentage of patients with at least one side effect
- Number and percentage of patients with at least one grade 3-4 side effect
- Number and percentage of patients with at least one SAE
- Number and percentage of patients with at least one side effect and grade 3-4 side effect due to the treatment.
- Number and percentage of patients with at least one side effect that lead to cessation of the treatment

Time to the first occurrence of grade 3-4 toxicity will be estimated by the Kaplan-Meier method.

XVII. POPULATIONS FOR ANALYSIS

The populations for the analysis are defined as follows:

Intention to treat: The intention to treat population will be composed by all included patients who were randomised to one of the two treatment groups, and patients will be analysed according to the treatment to which they were randomised. This will be the primary population for all analyses of efficacy data and baseline characteristics.

Per protocol: The per protocol population excludes patients randomised who did not receive any trial medication or who had a major violation of the protocol inclusion or exclusion criteria. Patients will be analysed according to the treatment to which they were randomised.

Safety: The safety population will include all patients who received at least one dose of trial medication. Only patients with clear documentation that no trial medication was received may be excluded. Patients will be analysed according to the treatment, which they actually received. This will be the population for the analysis of all safety data.

XVIII. ADVERSE EVENT REPORTING

1. Definition

An adverse event (AE) is defined as any untoward medical occurrence in a patient or clinical investigation subject administered a pharmaceutical product, which does not necessarily have a causal relationship with this treatment. An AE can therefore be any unfavourable and unintended sign (including an abnormal laboratory finding), symptom, or disease temporally associated with the use of a medicinal (investigational) product, whether or not related to the medicinal (investigational) product.

AE include the following:

- All suspected adverse medication reactions,
- All reactions from medication overdose, abuse, discontinuation, sensitivity, or toxicity.
- Apparently unrelated illnesses, including the worsening of a pre-existing illness.

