8.6.1.2 Serious adverse events

- A document will be produced by Pharmacovigilance.

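### The adverse-event window has two conflicting ends; on the longer one, deaths dominate the planned percentage of patients with an SAE and can mask a sunitinib excess

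*Protocol*

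**What the plan says.** - **Window.** Protocol XVIII.4 records "All AE that occur during the treatment period i.e. from the date of written informed consent to the final trial visit". It then adds later events only if the investigator judges them at least possibly related to study drug. The final trial visit is defined nowhere.
- **Treatment period elsewhere.** Protocol IX states "Total treatment duration will be one year (8 cycles"). Protocol XIX schedules quality of life "every 3 months the first year (treatment period"), so there the term means year one.
- **Follow-up.** Protocol XI continues visits every six months after year two without an end. Protocol XVI and SAP 5.5.3 plan about three years of follow-up after the last inclusion.
- **What counts.** Protocol XVIII.1 lists among AEs "Apparently unrelated illnesses, including the worsening of a pre-existing illness". Under XVIII.3.1 an untoward event is serious if, among other criteria, it "Results in death" or requires hospitalisation. XVIII.3.2 requires SAE reports whatever the presumed cause. Neither document exempts deaths or worsening due to HCC or cirrhosis.
- **What is tabulated.** Protocol XVI plans "Number and percentage of patients with at least one SAE", with no restriction to time on drug. For SAEs, SAP 8.6.1.2 says only "A document will be produced by Pharmacovigilance". By contrast, SAP 8.6.1.3 ties its percentage with grade 3-4 toxicity to TACE cycles and all treatment cycles.

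**The concern.** The same term covers two periods of very different length. If the SAE row follows the wording of XVIII.4 to the end of follow-up, it includes events before the first dose, events years after the drug was stopped, events under later anticancer treatment, and every death recorded up to the final visit. Overall survival is the phase III primary endpoint, and the plan expects most patients to die during follow-up. A patient who dies is already in the SAE row, so a non-fatal serious toxicity in that patient adds nothing to it. Fewer deaths on sunitinib would lower that arm's percentage for reasons unrelated to drug safety. Bleeding and liver failure are the plan's stated safety worries, so a reader could be misled by a row that looks like a plain comparison of serious toxicity.

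**Working it through.** **Inputs from the documents.** Two-year survival 40% on placebo and 60% on sunitinib; two-sided 5% error; 90% power; 130 deaths; 180 evaluable patients, taken as 90 per arm; uniform inclusion over 24 months; 36 months of follow-up after the last inclusion (Protocol XVI, SAP 5.5.3).

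**Assumptions.** Exponential survival. A non-fatal SAE risk s in each arm, independent of death. The documents give no s, so it is varied.

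**Step 1: reproduce the plan.** HR = ln(0.6)/ln(0.4) = 0.5575. Freedman's formula gives 131 deaths against the stated 130. The monthly hazards are λ = −ln(0.4)/24 = 0.03818 and −ln(0.6)/24 = 0.02128. With follow-up of 36 to 60 months,

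P(death) = 1 − (e^(−36λ) − e^(−60λ)) / (24λ).

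- Placebo: 1 − (0.2530 − 0.1012)/0.9163 = 0.834.
- Sunitinib: 1 − (0.4648 − 0.2789)/0.5108 = 0.636.
- Expected deaths: 90 × (0.834 + 0.636) = 132, which agrees with 130.

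Protocol II gives a study duration of 48 months instead. That implies follow-up of 24 to 48 months and only 114 deaths, so 60 months is the duration that fits the plan.

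**Step 2: the SAE row.** P(any SAE) = 1 − (1 − P(death)) × (1 − s). Over 13 months (12 on treatment plus an illustrative 1), P(death) is 1 − 0.4^(13/24) = 0.391 and 1 − 0.6^(13/24) = 0.242. With s = 20% on placebo and 40% on sunitinib:

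| Window and survival | Placebo | Sunitinib | Difference |
|---|---|---|---|
| To 60 months, design benefit | 1 − 0.166 × 0.8 = 86.7% | 1 − 0.364 × 0.6 = 78.2% | −8.6 |
| To 60 months, HR 1 | 86.7% | 1 − 0.166 × 0.6 = 90.1% | +3.3 |
| 13 months, design benefit | 1 − 0.609 × 0.8 = 51.3% | 1 − 0.758 × 0.6 = 54.5% | +3.2 |
| 13 months, fatal events shown apart | 20% | 40% | +20 |

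Differences are in points and were taken before rounding. In the first row, patients who died make up 0.834/0.867 = 96% of placebo patients with an SAE and 0.636/0.782 = 81% of those on sunitinib.

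**Step 3: vary s.** Placebo s runs from 10% to 40%, with a sunitinib excess of 10 to 30 points.

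- Long window with the design benefit: the row favours sunitinib throughout, by 1.0 to 14.2 points. For placebo s of 20%, sunitinib s would have to reach 64% before the arms were equal.
- 13 months with the design benefit: a 10-point excess still comes out reversed, by 1.4 to 5.9 points. An excess of 20 points or more stays visible, at +1.7 to +13.8 points. Break-even for placebo s of 20% is 36%.

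**The case against.** The strongest reply has four parts.

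- **The wording may mean one year.** XVIII.4 itself says treatment period, and its clause on later related events has little purpose if the window already covers all survival follow-up. This stands as a reason not to treat the long window as settled. It does not remove the conflict, and a 20-point excess is still compressed to about 3 points on the shorter window.
- **Progression is not automatically serious.** A reader might infer that the plan makes every HCC progression an SAE. It does not. Worsening becomes serious only through death, hospitalisation or another listed criterion, and the XVIII.1 item on worsening speaks of apparently unrelated illnesses. The figures above use deaths only.
- **Reversal is conditional.** In the 20% vs 40% illustration it needs both the long window and the full design benefit. At HR 1 the excess is diluted but keeps its direction. The toxicity rates and their independence from death are assumptions.
- **Toxicity is shown elsewhere.** Protocol XVI also plans treatment-related side effects, side effects leading to cessation, and time to first grade 3-4 toxicity. SAP 8.6.1.3 reports toxicity by cycle. The phase II endpoint covers one week after TACE, and the protocol expects only about 10 deaths around that analysis. No test or decision rule uses the SAE row, and the pharmacovigilance document may set its own window.

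The last part stands and limits the consequence. It does not repair the row: the treatment-related line does not mention SAEs, and attribution is difficult where cirrhosis can cause the same events.

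**Conclusion.** The window is defined inconsistently, and the SAE row has no on-treatment restriction in either document. On the literal long window, under the plan's survival assumptions, deaths alone put 83% of placebo and 64% of sunitinib patients in that row, a gap of about 20 points unrelated to non-fatal toxicity. An assumed 20-point sunitinib excess would then appear as roughly a 9-point advantage. It would appear as about a 3-point excess either with no survival benefit on the long window, or with the benefit on a window of about 13 months.

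A reader might go further and conclude that the SAE percentage must restate overall survival, or that the trial cannot detect sunitinib toxicity. The documents do not support that: the window is ambiguous, the survival benefit is a design assumption, and several other safety summaries are planned. What is established is that one descriptive safety figure could mislead and can be put right at little cost. The primary analysis is untouched.

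**What to change.** Leave AE collection and 24-hour SAE reporting as they are.

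1. Reconcile XVIII.4 with Protocol IX and XIX, and define the end of the AE window.
2. For the Protocol XVI incidence tables and the SAE summary, count events with onset from the first dose of study drug to a fixed interval after the last dose, or to the start of another anticancer treatment if earlier. The sponsor should set the interval before unblinding. State the same rule in SAP 8.6.1.2, so that the pharmacovigilance document follows it.
3. List events before the first dose and after the window separately.
4. Show the SAE percentage with and without fatal events of any cause and events due to HCC progression. All causes are needed because Protocol XVI expects a significant part of deaths to come from cirrhosis; removing only HCC deaths would leave those in the row.

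The cost is wording and tabulation. Protocol XVIII.2 already asks for onset dates, and separating all fatal events needs no judgement of cause. The HCC-progression line does need a cause classification, for which a short rule should be written. Late events move to a separate table. Because drug stops at progression (Protocol XV), time at risk may differ by arm, so the table should be read beside the treatment durations already planned in SAP 8.6.1.1.

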The Purpose of biomedical research involving human subjects must be to improve diagnostic, therapeutic and prophylactic procedures and the understanding of the aetiology and pathogenesis of disease.

In current medical practice most diagnostic, therapeutic or prophylactic procedures involve hazards. This applies especially to biomedical research.

Medical progress is based on research which ultimately must rest in part on experimentation involving human subjects.

In the field of biomedical research a fundamental distinction must be recognized between medical research in which the aim is essentially diagnostic or therapeutic for a patient, and medical research, the essential object of which is purely scientific and without implying direct diagnostic or therapeutic value to the person subjected to the research.

Special caution must be exercised in the conduct of research which may affect the environment, and the welfare of animals used for research must be respected.

Because it is essential that the results of laboratory experiments be applied to human beings to further scientific knowledge and to help suffering humanity, the World Medical Association has prepared the following recommendations as a guide to every physician in biomedical research involving human subjects. They should be kept under review in the future. It must be stressed that the standards as drafted are only a guide to physicians all over the world.

Physicians are not relieved from criminal, civil and ethical responsibilities under the laws of their own countries.

I. Basic

Principles

1. Biomedical research involving human subjects must conform to generally accepted scientific principles and should be based on adequately performed laboratory and animal experimentation and on a thorough knowledge of the scientific literature.
2. The design and performance of each experimental procedure involving human subjects should be clearly formulated in an experimental protocol which should be transmitted for consideration, comment and guidance to a specially appointed committee independent of the investigator and the sponsor provided that this independent committee is in conformity with the laws and regulations of the country in which the research experiment is performed.
3. Biomedical research involving human subjects should be conducted only by scientifically qualified persons and under the supervision of a clinically competent medical person. The responsibility for the human subject must always rest with a medically qualified person and never rest on the subject of the research, even though the subject has given his or her consent.
4. Biomedical research involving human subjects cannot legitimately be carried out unless the importance of the objective is in proportion to the inherent risk to the subject.
5. Every biomedical research project involving human subjects should be preceded by careful assessment of predictable risks in comparison with foreseeable benefits to the subject or to others. Concern for the interests of the subject must always prevail over the interests of science and society.
6. The right of the research subject to safeguard his or her integrity must always be respected. Every precaution should be taken to respect the privacy of the subject and to minimize the impact of the study on the subject's physical and mental integrity and on the personality of the subject.
7. Physicians should abstain from engaging in research projects involving human subjects unless they are satisfied that the hazards involved are believed to be predictable. Physicians should cease any investigation if the hazards are found to outweigh the potential benefits.
8. In publication of the results of his or her research, the physician is obliged to preserve the accuracy of the results. Reports of experimentation not in accordance with the principles laid down in this Declaration should not be accepted for publication.
9. In any research on human beings, each potential subject must be adequately informed of the aims, methods, anticipated benefits and potential hazards of the study and the discomfort it may entail. He or she should be informed that he or she is at liberty to abstain from participation in the study and that he or she is free to withdraw his or her consent to participation at any time. The physician should then obtain the subject's freely-given informed consent, preferably in writing.
10. When obtaining informed consent for the research project the physician should be particularly cautious if the subject is in a dependent relationship to him or her or may consent under duress. In that case the informed consent should be obtained by a physician who is not engaged in the investigation and who is completely independent of this official relationship.
11. In case of legal incompetence, informed consent should be obtained from the legal guardian in accordance with national legislation. Where physical or mental incapacity makes it impossible to obtain informed consent, or when the subject is a minor, permission from the responsible relative replaces that of the subject in accordance with national legislation. Whenever the minor child is in fact able to give a consent, the minor's consent must be obtained in addition to the consent of the minor's legal guardian.
12. The research protocol should always contain a statement of the ethical considerations involved and should indicate that the principles enunciated in the present Declaration are complied with.

II. Medical Research Combined with Professional Care (Clinical Research)

1. In the treatment of the sick person, the physician must be free to use a new diagnostic and therapeutic measure, if in his or her judgment it offers hope of saving life, reestablishing health or alleviating suffering.

2. The potential benefits, hazards and discomfort of a new method should be weighed against the advantages of the best current diagnostic and therapeutic methods.

3. In any medical study, every patient--including those of a control group, if any--should be assured of the best proven diagnostic and therapeutic method.
4. The refusal of the patient to participate in a study must never interfere with the physician-patient relationship.
5. If the physician considers it essential not to obtain informed consent, the specific reasons for this proposal should be stated in the experimental protocol for transmission to the independent committee (I,2).
6. The physician can combine medical research with professional care, the objective being the acquisition of new medical knowledge, only to the extent that medical research is justified by its potential diagnostic or therapeutic value for the patient.

III. Non-Therapeutic Biomedical Research Involving Human Subjects (Non-Clinical Biomedical Research)

1. In the purely scientific application of medical research carried out on a human being, it is the duty of the physician to remain the protector of the life and health of that person on whom biomedical research is being carried out.
2. The subjects should be volunteers--either healthy persons or patients for whom the experimental design is not related to the patient's illness.
3. The investigator or the investigating team should discontinue the research if in his/her or their judgment it may, if continued, be harmful to the individual.
4. In research on man, the interest of science and society should never take precedence over considerations related to the well-being of the subject.

ICH

HARMONIZED TRIPARTITE GUIDELINE E6: GOOD CLINICAL PRACTICE: CONSOLIDATED GUIDELINE

